1. LIST OF ABBREVIATIONS

AIC	Akaike Information Criterion
CHESS	CPRD-COPD Hawthorne Effect Study in Salford
CPRD	Clinical Practice Research Datalink
COPD	Chronic Obstructive Pulmonary Disease
EHR	Electronic Health Record
EMR	Electronic Medical Record
FEV1	Forced expiratory volume in 1 second
FF	Fluticasone furoate
FVC	Forced vital capacity
GOLD	Global Initiative for Chronic Obstructive Lung Disease
GPRD	General Practice Research Database
GP	General Practitioner
GSK	GlaxoSmithKline
HCU	Health Care Utilisation
HES	Hospital Episode Statistics
ICS	Inhaled Corticosteroid
ISAC	CPRD Independent Scientific Advisory Committee
LABA	Long Acting Bronchodilator
LAMA	Long Acting Muscarinic Antagonist
MHRA	Medicines and Healthcare Products Regulatory Agency
MPR	Medication Possession Ratio
MRC	Medical Research Council
NICE	National Institute for Health and Care Excellence
NWeH	North West eHealth
ONS	Office for National Statistics
PDC	Percent Days Covered
SAS	Statistical Analysis System
SES	Socio-Economic Status
SIR	Salford Integrated Record
SLS	Salford Lung Study
SOC	Standard of Care

WWEpi Project number: PRJ2282

SOP	Standard Operating Procedure	
UoM	University of Manchester	
VI	Vilanterol	

Trademark Information

Trademarks group of con		GlaxoSmithKline
RELVAR		

Trademarks	not	owned	by	the
GlaxoSmithK	line gr	oup of cor	npani	es
SAS				

WWEpi Project number: PRJ2282

Clinical Professor in Public Health Informatics, Health eResearch Centre, Farr Institute for Health Informatics Research, University of Manchester

PPD

Professor of Health eResearch, Health eResearch Centre, Farr Institute for Health Informatics Research, University of Manchester

PPD

Chief Clinical Officer, North West eHealth, Salford Royal Hospital

PPD

Professor of Clinical Epidemiology, London School of Hygiene and Tropical Medicine

PPD

Professor, Consultant in Respiratory Medicine, Department of Public Health, Section of Social Medicine, University of Copenhagen

PPD

Research Statistician, Clinical Practice Research Datalink

PPD

Head of Research, Clinical Practice Research Datalink

GSK Members:

PPD

Senior Director, Worldwide Epidemiology, Respiratory Therapeutic Area Lead, Worldwide Epidemiology GlaxoSmithKline

WWEpi Project number: PRJ2282

PPD

Global Medical Advisory Lead, Respiratory Franchise, GlaxoSmithKline

PPD

Director, Clinical Statistics, GlaxoSmithKline

WWEpi Project number: PRJ2282

ABSTRACT

Background: The Salford Lung Study (SLS) is a unique Phase IIIB pragmatic trial evaluating the effectiveness of a novel medicine – RELVAR (fluticasone furoate [FF], GW685698) and vilanterol [VI] GW642444) – compared with standard of care (SOC) among patients with Chronic Obstructive Pulmonary Disease (COPD). The trial is taking place in Salford, England. While the pragmatic nature of the trial is designed to test effectiveness in routine care, there are at least two possible concerns: 1) Salford may not be representative of the wider population in which the medicine may be used, and 2) there may be differences in local practice or changes to local practice caused by the study (the Hawthorne effect), which may artificially inflate the benefits of both RELVAR and SOC.

Objectives: The aim of the study is to evaluate the representativeness of Salford, and the potential Hawthorne effect, to place the SLS in wider context. The objectives are:

Co-primary objectives:

- PO1: To characterize the patients enrolled in the Standard of Care (SOC) arm of SLS COPD compared with the UK population of COPD patients (using the Clinical Practice Research Datalink (CPRD)), including distribution of SES/deprivation level, to evaluate the extent to which the SLS participants are representative of the UK patient population targeted for RELVAR. The comparator set will be specified on two bases: firstly, overall, and secondly, the subset fulfilling the protocol inclusion/exclusion criteria.
- PO2: To compare the rate of COPD exacerbation over the 12 months in Standard of Care arm of the SLS compared with the Standard of Care (SOC) recorded in the CPRD, in order to detect a potential Hawthorne effect.
- PO3: To compare the rate of serious pneumonia (defined by hospitalisation) over the 12 months in Standard of Care arm of the SLS compared with the Standard of Care recorded in the CPRD.

Secondary objectives:

- SO1: To make comparisons between the SLS SOC and the CPRD cohort on the following health care utilisation (HCU) endpoints: GP visits, hospital admissions, mortality and adherence.
- SO2: To evaluate other definitions of COPD exacerbations in SOC from CPRD.

WWEpi Project number: PRJ2282

 SO3: Self-controlled comparison of COPD and HCU endpoints in Salford before and after SLS commenced, using data from the SLS.

Study Design: Observational COPD cohort study, comparing Salford, UK (data source: SLS) with rest of UK (data source: CPRD) over a 12 month period.

Population: The setting is Salford, UK compared with rest of UK. The study population is, in Salford, participants recruited to the SLS and randomised to the SOC arm. In the rest of the UK, the comparison group is persons with COPD recorded in the CPRD who meet the eligibility criteria of the SLS.

Study Size: The target sample size for the SLS is 2,800. Study size in the CPRD will be based on the prevalence of COPD diagnosis codes; this will be a minimum 2,800 to match but is expected to be considerably larger (x5-10).

Analysis: Data analysis will use descriptive statistics for PO1. PO2 and PO3 will be addressed using multilevel modelling.

WWEpi Project number: PRJ2282

4. AMENDMENTS AND UPDATES

None.

5. MILESTONES

Deliverable	Timelines
Contract signed	November, 2014
Agreed Protocol for GSK protocol-review forum	November, 2014†
Completion of Statistical analyses plan.	November 2014 – 1st October 2015
Development of programs for analyses.	
"Data look" SLS data and CPRD data to UoM (Interim 1).	Jan 2016
Analyses of primary objectives (PO1 only) on subset of data using "data look" data (start working on PO2/3)	Feb-March 2016
Final SLS data (one year FU for all subjects) to UoM	1 st -8 th April 2016
Analyses of PO2 (COPD exacerbation data) using final SLS data: First report with P01/P02 to GSK	By 29 th April 2016
Share output from Primary Objectives with SLS Scientific Committee; and CHESS Steering Committee	9-10 th May 2016†
First manuscript developed and ready for submission with SLS paper to Thorax based PO1 and PO2 data	June-July 2016†
Programming for secondary objectives and PO3	May-October 2016
100% CPRD-HES data available to UoM (required for PO3 analyses).	Estimated at October 2016
Analysis for PO3 and draft tables circulated	November 2016
Draft complete study report with PO1/PO2/PO3 to GSK	December 2016†
Regulatory reporting of PO3	Q1 2017
Final follow-up manuscript	Q1-2 2017†

[†] Milestone payment

WWEpi Project number: PRJ2282

RATIONALE AND BACKGROUND

6.1. Background

Chronic Obstructive Pulmonary Disease (COPD) is a chronic obstructive disease of the airways associated with a significant social and healthcare burden [1, 2, 3]. Most patients with COPD are managed in primary care, as reflected in recent UK guidelines, which are specifically targeted at primary care physicians [4]. The major goals of treatment are to relieve symptoms, improve activity/exercise tolerance, prevent and treat exacerbations, reduce mortality risk and improve health status. However, despite such guidelines, COPD remains under-diagnosed and under-treated; variations in treatments, standards of care and adherence to guidelines have been reported across different geographical regions [2, 5, 6, 7, 8].

Large computerised patient databases provide a useful source of real life observational data, and the General Practice Research Database (GPRD) has been successfully used to generate descriptive epidemiology data in COPD [9, 10, 11, 12] from a large group of UK primary care practices. Historically, the limitations of the GPRD were a time gap between data capture and availability for the researcher and limited links to other healthcare databases, although these are currently being addressed with the development of the Clinical Practice Research Datalink (CPRD) and in recent Phase 4 pragmatic clinical trials [12]. The use of electronic medical record (EMR) data in health research is a key objective in the Department of Health's national research strategy [13].

The Salford Lung Study (SLS) is an ongoing Ph IIIB pragmatic trial comparing a new once daily ICS/LABA fixed dose combination (RELVAR: fluticasone furorate + vilanterol) in which patients are identified by EMR, enrolled in their GP office, randomized to RELVAR or Standard of Care (SOC) maintenance therapy and followed for safety and effectiveness via linked primary care/secondary routine care with primary endpoint of COPD moderate/severe exacerbations over 12 months [14]. MHRA and NICE provided joint advice for the SLS protocol and were supportive of the design to generate "real world" evidence which will demonstrate the value and safety of the medicine against the most relevant standard of care.

6.2. Rationale

Although the SLS will give evidence on the relative effectiveness of RELVAR compared with SOC, the SOC may be prone to the Hawthorne effect, which may distort the effect size.

The Hawthorne effect (also referred to as the observer effect) is a type of reactivity in which individuals improve or modify an aspect of their behaviour in response to their awareness of being observed. The original "Hawthorne effect" studies at the Hawthorne Works in Chicago, USA between 1924 and 1933 suggested that the novelty of being research subjects and the increased attention from such could lead to temporary increases in workers' productivity [15].

WWEpi Project number: PRJ2282

In the situation of this study, a potential Hawthorne effect may be a result of potentially different behaviours and decision making of GPs and nurses in their practices of caring for patients with COPD during the SLS study period.

Salford may not be representative of general UK population; hence the prognostic profiles, and potential effect of RELVAR in terms of the outcomes may differ in the general target COPD population compared with Salford.

Both of these issues mean that extrapolation of the results of the SLS to the wider UK population would be subject to major caveats. This proposal aims to explore, and assess how severe the caveats need to be.

RESEARCH QUESTION AND OBJECTIVE(S)

Co-primary objectives:

PO1: To characterize the patients enrolled in the Standard of Care (SOC) arm of the SLS compared with the UK population of COPD patients (using the Clinical Practice Research Datalink (CPRD)), including distribution of SES/deprivation level, to evaluate the extent to which the SLS participants are representative of the UK patient population targeted for RELVAR. The comparator set will be specified on two bases: firstly, overall, and secondly, the subset fulfilling the protocol inclusion/exclusion criteria.

PO2: To compare the rate of COPD exacerbation over the 12 months in Standard of Care arm of the SLS compared with the Standard of Care (SOC) recorded in the CPRD, in order to detect a potential Hawthorne effect or other differences.

PO3: To compare the rate of serious pneumonia (defined by hospitalisation) over the 12 months in Standard of Care arm of the SLS compared with the Standard of Care recorded in the CPRD.

Secondary objectives:

SO1: To make comparisons between the SLS Standard of Care and the CPRD cohort on the following health care utilisation (HCU) endpoints: GP visits, hospital admissions mortality and adherence.

SO2: To evaluate other definitions of COPD exacerbation in SOC from CPRD.

SO3: Self-controlled comparison of COPD and other HCU endpoints in Salford before and after SLS commenced.

WWEpi Project number: PRJ2282

8. RESEARCH METHODS

8.1. Study Design

This will be an observational COPD cohort study that will utilize the CPRD and the Salford EHR system – to compare selected cohorts with SLS.

For SLS, reference/index date is study entry. This will be matched in CPRD by the following algorithm:

1. Draw up a long-list of potentially eligible individuals in CPRD (patients who would be eligible at some point during the SLS recruitment phase).

2. For each individual:

- a. Randomly sample an entry date from full list of SLS entry dates.
- b. If patient is eligible at that entry date, then they will be included, accounting for relevant immortal time biases up to that entry date, otherwise, they will be excluded. Further details on methods of reducing immortal time bias (i.e left truncated at the entry date and survival modelling) will be outlined in the SAP.

First, the COPD populations in both Salford and in the wider CPRD (excluding Greater Manchester area) will be compared. Second, we will focus on comparisons between all patients enrolled in the SLS SOC arm versus a CPRD cohort that would have been eligible for SLS as per the inclusion and exclusion criteria.

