8.2.1. Inclusion Criteria

Two cohorts will be produced. First, a CPRD cohort, using linked primary care, medication, Hospital Episode Statistics, and socio-economic data, according to the following inclusion criteria:

- 1. Diagnosis of COPD before index date (time period will be defined in the SAP)
- 2. Aged ≥40 at index date.
- 3. Alive, and registered with a GP, at index date.
- 4. Not registered with a GP in the Greater Manchester area.

Second, a Salford cohort will be constructed using the Salford Integrated Record (SIR), according to the inclusion criteria:

- 1. Diagnosis of COPD before index date.
- 2. Aged ≥40 at index date.

WWEpi Project number: PRJ2282

3. Alive, and registered with a GP, at index date.

Restricted cohorts will then be constructed in both the Salford and CPRD populations, based on the inclusion/exclusion criteria and study period for the SLS:

- Patients with documented GP diagnosis of COPD, and currently receiving maintenance therapy
- 2. Male or female subjects aged ≥40 years of age at index date
- 3. Patients who have a history of treatment with systemic/oral corticosteroids, antibiotics (in association with GP contact) and/or hospitalisation for at least one COPD exacerbation in the 3 years prior to index date.
- 4. Current COPD Therapy

All patients currently receiving either:

- inhaled corticosteroid (ICS) alone or in combination with a long acting bronchodilator (this could be a fixed dose combination or an ICS/LABA provided in two separate inhalers, or ICS and LAMA),
- or long-acting bronchodilator therapy alone (e.g. tiotropium or salmeterol, or the use of two bronchodilators i.e. LABA/LAMA),
- or "triple therapy" i.e. ICS/LABA plus a Long Acting Muscarinic Antagonist (LAMA)

Finally, the third data source, the SLS, will be used as-is.

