8.2.2. Exclusion Criteria

Subjects meeting any of the following criteria must not be included in the restricted cohorts:

- 1. Patients with any life threatening condition or uncontrolled/clinically significant disease (code list to be specified in the Study Analysis Plan)
- Patients with unstable COPD: Patients with an exacerbation (defined by treatment with oral corticosteroids and/or antibiotic or hospital discharge listing COPD) with an onset within 2 weeks of index date. Delay index date until at least 2 weeks after the onset of an exacerbation and until the exacerbation has resolved.
- Chronic user of oral corticosteroids: Subjects who are considered to be a chronic user of oral corticosteroids for respiratory or other indications (Algorithm to be specified in the Study Analysis Plan).
- 4. In the Salford population only, those patients who are entered in the SLS and randomised to the RELVAR arm.

WWEpi Project number: PRJ2282

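### Sections 8.1 and 8.2.2 give conflicting index-date rules for CPRD patients with a recent exacerbation, and the literal 8.1 rule lowers the crude PO2 comparator rate

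*Protocol*

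**What the plan says.** Section 8.1 (Study Design) builds the CPRD cohort in two steps. The long-list holds "patients who would be eligible at some point during the SLS recruitment phase". Step 2a then says "Randomly sample an entry date from full list of SLS entry dates", one date per patient. Under step 2b a patient eligible on that date enters, with allowance for immortal time "up to that entry date, otherwise, they will be excluded". No second draw and no deferral is mentioned. What 8.1 leaves to the SAP is the method for reducing immortal time bias, not this rule.

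Section 8.2.2 (Exclusion Criteria), criterion 2, concerns an exacerbation "with an onset within 2 weeks of index date". It does not stop at exclusion, but adds: "Delay index date until at least 2 weeks after the onset of an exacerbation and until the exacerbation has resolved".

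Section 8.2.1 shows where that criterion applies: "Restricted cohorts will then be constructed in both the Salford and CPRD populations", on the basis of the SLS criteria. The trial data are treated differently: "Finally, the third data source, the SLS, will be used as-is". Their index date is actual study entry.

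The outcome at stake is PO2: "To compare the rate of COPD exacerbation over the 12 months in Standard of Care arm of the SLS", set against CPRD standard of care.

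**The concern.** Take a CPRD patient whose exacerbation began 10 days before the drawn date. Under 8.1 the patient is lost. Under 8.2.2 the patient enters a little later. Two programmers working from this protocol could build different comparators.

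The difference is not random with respect to the outcome. The more often a patient exacerbates, the more likely a random date falls within 2 weeks of an onset. Step 2b, read literally, therefore thins out frequent exacerbators, and PO2 compares exacerbation rates. SLS patients do not pass through step 2b. If SLS recruitment deferred such patients and later enrolled them, the crude CPRD rate would be low relative to SLS. The SLS rate would look higher by comparison, and a Hawthorne reduction would be harder to see.

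**Working it through.** The protocol gives no exacerbation rate, dispersion or power figure on this point, so there is no stated figure to reproduce. The check has three parts.

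**1. Chance of being dropped under step 2b**

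Input from the protocol: window w = 14 days = 14/365.25 = 0.0383 years (8.2.2, criterion 2). For a patient with a constant rate r per year:

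P(dropped) = 1 − exp(−r·w)

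| Patient's rate per year | P(dropped) |
|---|---|
| 0.33 | 1.3% |
| 1 | 3.8% |
| 2 | 7.4% |
| 4 | 14.2% |
| 6 | 20.5% |

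For example, at 4 per year: 1 − exp(−4 × 0.0383) = 14.2%. The loss rises almost in proportion to the rate. Under the 8.2.2 delay nobody is lost on this ground.

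**2. Effect on the crude comparator rate**

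Assumptions, not in the documents: patient rates follow a gamma distribution with mean m = 1.5 to 2 per year and shape s = 0.5 to 2, and events are Poisson given the rate. Without any entry criterion:

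mean rate of those kept ÷ mean rate of all = 1/(1 + m·w/s)

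| Mean m | s = 2 | s = 1 | s = 0.5 |
|---|---|---|---|
| 1.5 | 2.8% low | 5.4% low | 10.3% low |
| 2.0 | 3.7% low | 7.1% low | 13.3% low |

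For example, m = 2 and s = 0.5: 1/(1 + 2 × 0.0383/0.5) = 1/1.153 = 0.867, or 13.3% low.

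Section 8.2.1 also requires at least one exacerbation in the previous 3 years. Simulating the six scenarios with that criterion, 6% to 10% of otherwise eligible patients are dropped. The ratio of kept to all runs from 0.975 (m = 1.5, s = 2) to 0.887 (m = 2, s = 0.5), so the crude rate is about 2.5% to 11% too low.

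A separate run with wider assumed ranges (mean 1.0 to 2.5 per year, shape 1/1.2 to 1/0.3) gave 1% to 9% low for 14 days. It gave 2% to 17% low if 28 days is assumed to cover resolution; the protocol states only the 2 weeks.

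**3. What the planned adjustment recovers**

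Section 8.3.3 lists previous COPD exacerbation as a covariate, and the PO2 model in 8.7.1 starts from all listed covariates. In the same six scenarios, the rate in those kept was compared with the rate in all patients after adjustment for exacerbations in the prior 12 months:

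| Coding of the covariate | Ratio kept/all | Remaining bias |
|---|---|---|
| Not adjusted | 0.975 to 0.887 | 2.5% to 11% |
| Any/none | 0.983 to 0.907 | 2% to 9% |
| Five categories (0 to 4+) | 0.998 to 0.961 | 0.2% to 4% |
| Full count | 1.00 | none |

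The last row has a simple reason. With a constant rate, once the number of events in the year is known, their timing says nothing more about the rate. Being free of events in the last 14 days is then uninformative. Coarser coding mixes patients with different counts in one category, and those dropped are the ones with the higher counts.

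**The case against.** The strongest reply is that the two sections can be read together. Section 8.2.1 first builds a broad CPRD cohort (diagnosis, age, alive and registered, outside Greater Manchester) and only then the restricted ones. Eligibility in step 2b could refer to the broad criteria, with 8.2.2 moving the date afterwards, or it could include the delay clause. On either reading nobody is lost. This stands in part: permanent exclusion is the literal reading of 8.1, not a settled plan to remove frequent exacerbators. But step 2b says nothing about moving the date, and no sentence gives 8.2.2 precedence, so the conflict remains.

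A reader might infer that adjustment cannot recover the loss because the patients removed are the extreme tail. The calculation does not support that: the full prior-year count removes the bias under this model. What is left depends on coding, which 8.3.3 assigns to the SAP.

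A reader might also infer that a true Hawthorne reduction will be masked. The documents do not show this. The percentages in part 2 concern the crude rate. The PO2 decision in 8.7.1 asks whether the SLS random effect falls outside the 2.5 to 97.5 percentile range, and no between-region spread is given against which to judge the shift. Nor does the protocol describe SLS enrolment practice. That SLS kept deferred patients is inferred from the 8.2.2 criteria being based on those of the SLS. If some deferred patients never returned, SLS carries part of the same selection and the difference shrinks.

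**Conclusion.** The concern holds as an unreconciled contradiction between section 8.1, step 2b, and section 8.2.2, criterion 2, that bears on a co-primary comparison. Read literally, step 2b selects on the outcome, and the direction is the same in every scenario: the crude CPRD rate falls. The size depends on the assumed mean and spread of patient rates and on a constant rate within each patient; any effect on the SLS contrast also depends on SLS having deferred and kept such patients. The bias in the PO2 estimate itself could be anything from nothing to about 9%, depending on how previous exacerbation is coded. Severity is moderate: the text should be settled before the cohort is built, but the protocol does not show that the PO2 conclusion would change.

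**What to change.** Reconcile 8.1 and 8.2.2 so that one index-date rule applies to CPRD patients with a recent exacerbation. One way is to add to step 2b that, when this is the only unmet criterion on the drawn date, the 8.2.2 delay applies: the index date moves within the SLS recruitment window, the other criteria are re-checked on the new date, and the patient is retained. All other failures would still lead to exclusion. Also state that previous exacerbation enters the PO2 model as a prior-year count, not as any/none or a few categories.

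The cost is one sentence in 8.1, a few lines of cohort-building code and the definition of one covariate. No new data are needed.

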8.2. Setting

In terms of geography, Salford, UK, and surrounding areas within Greater Manchester, for the SLS group; UK-wide, excluding Greater Manchester, for the CPRD group. In terms of health settings, general practice – restricted to practices in Salford and to practices that contribute to CPRD (~10%).

